8.1.2. Definition of an Adverse Device Effect

An adverse device effect is an adverse event related to the use of an investigational medical device or a combination product. This includes adverse events resulting from insufficient or inadequate instructions for use, deployment, implantation, installation, operation, or any malfunction of the investigational medical device, including any event resulting from user error or from intentional misuse of the investigational medical device. This definition includes events related to the procedures involved. For users or other persons, this definition is restricted to events related to investigational medical devices.

8.1.3. Recording and Reporting of Adverse Events

For recording of adverse event, the study period is defined for each patient as the time period from signature of the ICF to the end of study (ie, patient's last visit). Treatment-emergent adverse events are defined as adverse events that occurred after the first dose of IMP and/or device was administered through the end of the study.

All adverse events that occur during the defined study period must be recorded both on the source documentation and the CRF, regardless of the severity of the event or judged relationship to the IMP and/or device. For serious adverse events and PDAESI for expedited reporting to GPSP, the serious adverse event and PDAESI form must be completed and the serious adverse event and the PDAESI must be reported immediately (Section [8.1.8.1](#)). The investigator does not need to actively monitor patients for new adverse events after the end of the study.

At each contact with the patient, the investigator or designee must question the patient about adverse events by asking an open-ended question such as "Have you had any unusual symptoms or medical problems since the last visit? If yes, please describe." All reported or observed signs and symptoms will be recorded individually, except when considered manifestations of a medical condition or disease state. A precise diagnosis will be recorded whenever possible. When such a diagnosis is made, all related signs, symptoms, and any test findings will be recorded collectively as a single diagnosis on the CRF and, if it is a serious adverse event or PDAESI for expedited reporting to GPSP, on the serious adverse event and PDAESI form.

The clinical course of each adverse event will be monitored at suitable intervals until resolved, stabilized, or returned to baseline; or until the patient is referred for continued care to a health care professional; or until a determination of a cause unrelated to the IMP and/or device or study procedure is made.

The onset and end dates, duration (in case of adverse event duration of less than 24 hours), action taken regarding IMP and/or device, treatment administered, and outcome for each adverse event must be recorded both on the source documentation and the CRF.

The relationship of each adverse event to IMP (including to the device, if applicable), and the severity and seriousness of each adverse event, as judged by the investigator, must be recorded as described below in Section [8.1.5](#).

[figure not shown]
Further details are given in the Safety Monitoring Plan.

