
A secondary objective of the study is to evaluate the safety and tolerability of 2 different doses of TEV-48574 sc administered Q2W in adult patients with IBD (moderate to severe UC or CD).
	
The safety and tolerability measures/parameters are as follows:
 
 • Adverse events • Change from baseline in clinical laboratory test results (serum chemistry, hematology, and urinalysis) • Change from baseline in vital signs measurements (blood pressure, pulse rate, body temperature, and respiratory rate) • Change from baseline in 12-lead electrocardiogram findings • Patients who stopped the investigational medicinal product due to adverse events • Local tolerability at the injection site

A secondary objective of the study is to evaluate the immunogenicity of 2 different doses of TEV-48574 sc administered Q2W in adult patients with IBD (moderate to severe UC or CD).
	
The immunogenicity endpoints for this study are as follows:
 
 • Change from baseline in treatment-emergent anti-drug antibody (ADA) at weeks 2, 4, 8, 14, and follow-up visit • Presence of neutralizing ADA in ADA positive patients at weeks 2, 4, 8, 14, and follow-up visit

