Patients randomized prior to Amendment 03 with Revision 01 will continue to receive the same dose, volume, and rate of administration of the IMP to which they were initially randomized and will remain blinded.

Treatment and Follow-Up Period: During the 14-week treatment period, patients will visit the site Q2W on days 1, 15, 29, 43, 57, 71, and 85 (± 3 days) for IMP administration (7 visits), as well as an end-of-treatment visit on day 99 (± 3 days; week 14) ([Table 1](#)). After the end of the

14-week treatment period, all patients may be offered the option to enter a long-term extension study, which is described in a separate protocol (TV48574-IMM-20038). If they choose to enter (sign the extension study informed consent form [ICF]) and will subsequently be randomized into the long-term extension study, they will not need to complete the follow-up visit in this study. All other patients will return to the site for a follow-up visit (day 127 [± 3 days]). For those patients who enter the long-term extension study, adverse events and concomitant medication data will be recorded in the dose-ranging study case report form (CRF) up until the date of extension study randomization (defined as the study completion date for the dose-ranging study). For those patients who screen fail the long-term extension study, adverse events and concomitant medication data will be recorded in the dose-ranging study up until the follow-up visit (day 127 [± 3 days]) CRF. Patients who complete the last scheduled visit will be considered to have completed the study.

Patients who withdraw from the study before completing the 14-week treatment period will complete the assessments for the early termination visit and will be encouraged to complete the follow-up period in the study.

The end of study is defined as the last visit of the last patient.

The total duration of patient participation in the study is planned to be up to 24 weeks for each individual patient.

The study duration will be approximately 27 months, from Q3 2022 until approximately Q4 2024.

Study procedures and assessments with respective time points are shown in [Table 1](#).

The overall study schematic diagram is shown in [Figure 1](#).

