6.6.3. Permitted Inflammatory Bowel Disease Medications and Rescue Medications

Permitted concomitant treatment for UC and CD must remain at a stable dose (no increase or decrease) during the study treatment period (except for decreases due to adverse events); if doses are increased, patients must be withdrawn from the study. The dose of any background medication for UC and CD should not be changed during the screening and double-blind treatment period. If a patient requires initiation of a new therapy for UC or CD, the patient should be withdrawn from the study, and appropriate treatment should be administered at the discretion of the investigator.

Patients will be allowed to use the following medications as detailed below:

- Concomitant use of oral 5-ASA or sulfasalazine. Dose must be stable for at least 4 weeks prior to endoscopy and through week 14. If oral 5-ASA treatment has been recently discontinued, it must have been stopped for at least 2 weeks prior to endoscopy.
- A stable dose of oral corticosteroids (prednisone equivalent of up to 20 mg/day; budesonide of up to 9 mg/day) for at least 2 weeks prior to endoscopy and through week 14. If oral corticosteroids have been recently discontinued, they must have been stopped at least 2 weeks prior to endoscopy. Decreases in steroid use due to adverse events are allowed.
- A stable dose of immunosuppressant drugs (methotrexate, 6-MP, or AZA consistent with regional standard of care) for 4 weeks prior to endoscopy and through week 14. Decreases due to adverse events are permitted.

Following the week 14 visit if not continuing on to the long-term extension study, patients will no longer need to abstain from the medications that were prohibited or required no change in dose during the screening and induction period. Biologic treatment(s) should not be initiated during the follow-up period without discussion with the sponsor.

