10.8. Tolerability Analysis

Tolerability will be assessed by the number (%) of patients who fail to complete the study due to adverse events.

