11 MAR 2024

Dear Investigator:

The purpose of this letter is to provide clarification that patients enrolled in France will not be offered the option to enter in the long-term extension study (TV48574-IMM-20038). Therefore, the statement “After the end of the 14-week treatment period, all patients may be offered the option to enter a long-term extension study (to be described in a separate protocol [TV48574-IMM-20038])”, which is noted in the protocol sections below, is not applicable for patients enrolled in France.

- Protocol Synopsis: “Treatment and Follow-Up Period” and “Plans for Treatment or Care after the Patient Has Ended Participation in the Study”
- Section 3.1. General Study Design and Study Schematic Diagram: “Treatment and Follow-Up Period”
- Figure 2: Overall Study Schematic Diagram
- Table 4: Study Procedures and Assessments
- Section 5.4 Treatment After the End of the Study

After the end of the 14-week treatment period, those patients enrolled in France will return to the site for a follow-up visit at week 18 (day 127 [± 3 days]) as specified in Table 4 (Study Procedures and Assessments) of the protocol.

These changes will be incorporated into the protocol during the next amendment, as applicable. Please ensure that this letter is maintained with the study protocol. Also, please provide a copy of this letter to your IRB/IEC for review and acknowledgement.

Please feel free to contact [REDACTED] if you have any questions or concerns regarding this letter.

Sincerely,

[Redacted signature area]

11-Mar-2024 | 23:02 GMT

[Redacted signature area]

Country-Specific Requirements: Japan

The following country-specific requirements are applicable to all subjects enrolled at study centers in Japan.

Revised Text is captured in the format ~~strikethrough=deleted text~~; underline=new text.

Amendment 04 (JP 05) (ES 01) (FR 01): Local Administrative Letter 01
Dated 12 March 2024**LOCAL ADMINISTRATIVE LETTER 01 FOR JAPAN (JP)**

Study number: TV48574-IMM-20036

Clinical Study Protocol TV48574-IMM-20036 Protocol Am 03 with Rev 01 (JP 04) (ES 01)

A 14-Week Phase 2b, Randomized, Double-Blind, Dose-Ranging Study to Determine the Pharmacokinetics, Efficacy, Safety, and Tolerability of TEV-48574 in Adult Patients with Moderate to Severe Ulcerative Colitis or Crohn's Disease (RELIEVE UCCD) 1

21 September 2023

IND number: **157634**; NDA number: **Not applicable**; EudraCT number: **2021-006881-19**.

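### Section 10.8 measures tolerability by study non-completion although the endpoint is stopping IMP for adverse events; secondarily, the treatment-emergent window differs by extension entry

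*Protocol*

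**What the plan says.** **Tolerability.** Protocol Section 3.1 lists among the secondary safety and tolerability measures "Patients who stopped the investigational medicinal product due to adverse events". The synopsis lists the same item. Section 10.8, the only text on tolerability analysis, reads "Tolerability will be assessed by the number (%) of patients who fail to complete the study due to adverse events". Section 10.7 summarises and lists adverse events that cause withdrawal from the study. Section 5.3 allows a patient to stop IMP and remain in the study for assessments. Section 10.4.1 tabulates IMP discontinuations by reason, as part of disposition.

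**Window.** Section 8.1.3 defines treatment-emergent events as "adverse events that occurred after the first dose of IMP and/or device was administered through the end of the study", and sets the recording period for each patient as "the time period from signature of the ICF to the end of study (ie, patient's last visit". Under Section 4.1, a patient who enters the extension skips the follow-up visit, and events are recorded "up until the date of extension study randomization (defined as the study completion date for the dose-ranging study". All others, including those who fail extension screening, are recorded to the follow-up visit on day 127. The French letter in Appendix M says "patients enrolled in France will not be offered the option to enter in the long-term extension study". After week 14, for those not continuing, Section 6.6.3 says "patients will no longer need to abstain from the medications that were prohibited", although biologics should not be started without discussion with the sponsor. Section 10.7 counts each patient once per term and states neither an exposure adjustment nor a common cut-off.

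**The concern.** The tolerability analysis does not measure its own endpoint. Stopping IMP and leaving the study are different events in this protocol, and Sections 10.7 and 10.8 both count the second. A patient who stops IMP because of an adverse event but attends the remaining visits has met the endpoint and is absent from both analyses. In a dose-ranging study, the share of patients who could not continue a dose is a figure that people will look for when choosing the next dose.

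The window point is of the same kind: a study-level definition where a treatment-level one is needed. How long a patient is observed depends on a choice made after randomisation. If the arms differ in how often patients enter the extension, crude percentages compare groups with different time at risk. The beta-binomial safety rules in Appendix L also compare crude event rates, active against placebo. There is also a wording ambiguity: Section 4.1 says "The end of study is defined as the last visit of the last patient", so the term that closes the treatment-emergent window has two meanings.

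**Working it through.** **1. Tolerability: the passages side by side**

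| Patient | Endpoint, Section 3.1 | Section 10.8 | Section 10.7 withdrawal summaries | Section 10.4.1 disposition |
|---|---|---|---|---|
| Stops IMP for an adverse event and leaves the study | counted | counted | counted | shown |
| Stops IMP for an adverse event and stays to the last scheduled visit | counted | not counted | not counted | shown |

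The second row is possible under Section 5.3. Section 4.1 treats a patient who attends the last scheduled visit as a completer. Conversely, a patient who received all seven doses and then left during follow-up because of an adverse event would be counted by Section 10.8 without having stopped IMP.

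Illustration (assumed counts; the planned 40 UC + 40 CD per dose arm gives 80): 4 patients stop IMP for an adverse event and 2 of them stay. The endpoint is 4/80 = 5.0%; Section 10.8 gives 2/80 = 2.5%.

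**2. Window length**

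- The stated maximum participation is reproduced: 42/7 + 14 + 4 = 24 weeks.
- From first dose: day 99 − day 1 = 98 days for an entrant randomised to the extension at week 14, and day 127 − day 1 = 126 days for others. 126/98 = 1.29. If extension randomisation falls after week 14, the gap is smaller.
- From the last dose on day 85: 14 v 42 days. Section 8.3 takes 5 half-lives as 50 days, so neither window covers that period.

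**3. What this could do to a between-arm comparison**

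Assumptions: constant event hazard, no drug effect, and shares entering the extension of f_A (active) and f_P (placebo). The protocol gives no entry rates, so the split is assumed.

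- Week 18 incidence: I18 = 1 − (1 − I14)^(126/98)
- Arm incidence: f × I14 + (1 − f) × I18
- Active minus placebo: −(f_A − f_P) × (I18 − I14)

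| I14 | I18 | Equal entry | 90% v 50% | Extreme, 100% v 0% |
|---|---|---|---|---|
| 5% | 6.4% | 0 | −0.6 points | −1.4 |
| 10% | 12.7% | 0 | −1.1 | −2.7 |
| 30% | 36.8% | 0 | −2.7 | −6.8 |
| 50% | 59.0% | 0 | −3.6 | −9.0 |

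For example, in the last row: 0.9 × 0.50 + 0.1 × 0.590 = 0.509 against 0.5 × 0.50 + 0.5 × 0.590 = 0.545. Reversing the entry shares reverses the sign.

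**4. Effect on the safety rule**

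This uses Beta(1,1) priors, 40 per arm, the 0.90 cutoff, week 14 incidence of 30%, no drug effect, and one look at the end of the study. The same exact calculation, without an interim, gives success probabilities of 7.9% (null) and 91.0% (efficacy) for UC and 9.6% and 87.2% for CD. Table 10 states 8% and 91% for UC, and 9 to 10% and 87% for CD.

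- Equal entry (80% in each arm): the rule is met with probability 9.7%.
- 90% active v 50% placebo: 6.0%.
- 50% active v 90% placebo: 15.0%.

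**The case against.** A reader might infer that the safety comparison is unequal and favours TEV-48574 because patients who benefit roll over. The documents do not support that. The extension may be offered to all patients, is not tied to response, and is chosen while patients and sites are blinded (Section 6.9.2). Non-responders may choose it just as readily. The French exception applies to every arm alike. Nor is a surge of flare events in weeks 14 to 18 to be expected from the text: Section 8.1.1 keeps IBD manifestations out of adverse events unless they are worse than the patient's usual course, and Section 6.6.3 restricts new biologics. All of this stands, so the between-arm effect is a possibility of unknown sign.

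It can also be said that an analysis window is ordinary SAP content and that onset dates are recorded, so nothing is lost. That is fair and is why the window point is secondary. The protocol does, however, fix the treatment-emergent definition itself. The possible effect is also modest against sampling error: at 50% incidence the standard error of a difference is √(2 × 0.25/80) = 7.9 points with 80 per arm and √(2 × 0.25/40) = 11.2 points with 40.

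On tolerability, Section 10.4.1 does report IMP discontinuation by reason. Some reasons for stopping IMP also take the patient out of the study: increases in IBD medication or new IBD therapy (Section 6.6.3), surgery (Section 6.6.4), and permanent liver-related stops, which lead to the early termination visit (Appendix K). This limits how many patients are missed. It does not make Section 10.8 an analysis of the Section 3.1 endpoint.

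**Conclusion.** The tolerability mismatch holds on the text and needs no assumption. Sections 10.8 and 10.7 count study withdrawal for adverse events, the endpoint is IMP discontinuation for adverse events, and Section 5.3 makes the two separable. The number affected cannot be known in advance; 2.5% against 5% is an illustration only.

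The window point holds in a limited form. Up to 28 days of observation depend on extension entry. Crude incidences can differ between arms only if entry does: about 0.6 to 3.6 points in either direction under an assumed 90% v 50% split, and nothing if entry is equal. These figures rest on a constant hazard and on entry rates that the protocol does not give.

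**What to change.** 1. In Section 10.8, define tolerability as the number and percentage of patients who discontinue IMP because of adverse events. Make the same change in the matching Section 10.7 summaries and listings, and keep study withdrawal for adverse events as a separate row. This is a wording change.
2. Keep the full-window adverse event tables and add a between-arm summary over a window common to all patients, from first dose to the date of the day 99 visit regardless of IMP discontinuation, or exposure-adjusted rates. Show later events separately as follow-up. This should be an addition and not a replacement, because day 99 is only 14 days after the last dose while Section 8.3 takes 5 half-lives as 50 days. A cut tied to each patient's last dose would again make the window depend on a post-randomisation event.
3. In Section 8.1.3, say that the window closes at the patient's own last visit or extension randomisation date, so that it cannot be read as the last visit of the last patient.

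Cost: one extra table split and no new data.

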8.1.4. Recording and Reporting of Adverse Device Effect

Adverse device effects ([Figure 3](#)) must be recorded on both the source documentation and the CRF.

The investigator and sponsor will record all relevant information regarding every adverse device effect/serious adverse device effect and device deficiency.

The investigator should make an initial determination whether the adverse event may be related to a device deficiency.

Figure 3: Decision Tree for Adverse Events and Adverse Device Effects Classification

ADE=adverse device effect; AE=adverse event; CRF=case report form; IEC=Independent Ethics Committee; IRB=Institutional Review Board; SADE=serious adverse device effect; SAE=serious adverse event.

8.1.5. Severity of an Adverse Event

The severity of each adverse event must be recorded. The adverse event severity grading scale for the current version of the National Cancer Institute Common Terminology Criteria for Adverse Events (NCI CTCAE; version 5) will be used for assessing adverse event severity.

Table 4 will be used for assessing severity for adverse events that are not specifically listed in the NCI CTCAE.

Table 4: Adverse Event Severity Grading Scale for Events Not Specifically Listed in NCI CTCAE

Grade	Severity
1	Mild; asymptomatic or mild symptoms; clinical or diagnostic observations only; intervention not indicated.
2	Moderate; minimal, local or noninvasive intervention indicated; limiting age-appropriate instrumental activities of daily living. ^a
3	Severe or medically significant but not immediately life-threatening; hospitalization or prolongation of hospitalization indicated; disabling; limiting self-care activities of daily living. ^{a,b}
4	Life-threatening consequences; urgent intervention indicated.
5	Death related to adverse event (AE).

^a Instrumental activities of daily living refer to preparing meals, shopping for groceries or clothes, using the telephone, managing money, etc.

^b Examples of self-care activities of daily living include bathing, dressing and undressing, feeding oneself, using the toilet, and taking medications, as performed by patients who are not bedridden.

Note: Based on the most recent version of NCI CTCAE (v5.0), which can be found at:

https://ctep.cancer.gov/protocoldevelopment/electronic_applications/docs/CTCAE_v5_Quick_Reference_8.5x11.pdf.

8.1.6. Relationship of an Adverse Event to the Investigational Medicinal Product and/or Device

The relationship of an adverse event to the IMP and/or device is characterized as follows:

Table 5: The Relationship of an Adverse Event to the Investigational Medicinal Product and/or Device

Term	Definition	Clarification
No reasonable possibility (not related)	This category applies to adverse events that, after careful consideration, are clearly due to extraneous causes (disease, environment, etc) or to adverse events that, after careful medical consideration at the time they are evaluated, are judged to be unrelated to the IMP and/or device.	The relationship of an adverse event may be considered “no reasonable possibility” if it is clearly due to extraneous causes or if at least 2 of the following apply: 
 • It does not follow a reasonable temporal sequence from the administration of the IMP and/or device. • It could readily have been produced by the patient’s clinical state, environmental or toxic factors, or other modes of therapy administered to the patient. • It does not follow a known pattern of response to the IMP and/or device. • It does not reappear or worsen when the IMP and/or device is re-administered.
Reasonable possibility (related)	This category applies to adverse events for which, after careful medical consideration at the time they are evaluated, a connection with the administration of IMP and/or device cannot be ruled out with certainty.	The relationship of an adverse event may be considered “reasonable possibility” if at least 2 of the following apply: 
 • It follows a reasonable temporal sequence from administration of the IMP and/or device. • It cannot be reasonably explained by the known characteristics of the patient’s clinical state, environmental or toxic factors, or other modes of therapy administered to the patient. • It disappears or decreases on cessation or reduction in dose. There are important exceptions when an adverse event does not disappear after discontinuation of the IMP and/or device, yet an IMP and/or device relationship clearly exists. • It follows a known pattern of response to the IMP and/or device.

IMP=investigational medicinal product.

